Background	
Genital herpes has a high prevalence in industrialized as well as developing countries.
 
Genital herpes causes genital ulcers, increases risk for acquiring HIV infection, and may be transmitted mother to child during birth with possible serious consequences.
 
Medical treatments and condoms only partially reduce the risk for transmission from/ to sexual partners. Genital herpes transmission despite use of condoms is thought to be due to transfer via skin-to-skin contact in unprotected areas, and HSV-2 transmission may be enhanced by current shaving habits in the genital area leading to micro lesions (lacerations) of the skin.
 
VIBLOK™ is a cream designed to impede the passage of viruses, such as HSV-2, across the skin. Bench and animal experiments indicate that it can block virus transmission (HIV, HPV, HSV) up to 98%.
 
The objective of this clinical trial is to assess the safety and performance of VIBLOK in adults with HSV-2 infection by comparing virus detection in the extra-genital area before and after application of the barrier cream.

Primary objective	To assess safety of VIBLOK in HSV-2 infected adults.
Secondary objective	To evaluate the performance of VIBLOK as a barrier for virus transmission in men and women.
Study design	The VIBLOK SAfety and perFormancE Trial is a prospective, non-randomized, comparative multi-center safety and performance study. Up to 84 adults with a suspected HSV-2 infection are planned to be enrolled at up to 6 participating investigational centers in The Netherlands and Germany. Participants with a confirmed HSV-2 infection are planned to be followed for 26-31 days, using VIBLOK for minimally 26 days in a row. Safety will be assessed by collecting all adverse events, and HSV will be measured from daily self-collected external genital swabs before and after application of VIBLOK.
Study device	VIBLOK cream
Study scope	Minimally 1 and maximally 6 sites in The Netherlands and Germany are

	planned to participate in this study.
Study duration	The study is anticipated to last 12 months from first-subject-in to last-subject-out. Study participants are planned to be followed for 26 to 31 days.
Study Population	Adults with recurrent genital HSV-2 infections that meet all the inclusion and none of the exclusion criteria.
Number of subjects	Up to 84 men and women are to be enrolled, ensuring 46 participants with confirmed eligibility applying VIBLOK.

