4.1. Inclusion Criteria

Candidates for this study must meet **all** of the following inclusion criteria:

1. Participant is male or female and at least 18 years of age
2. HSV-2 seropositive by the UW Western blot or Alegria assay
3. History of recurrent genital herpes with at least 3 recurrences in the last year or, if currently on suppressive/ prophylactic therapy, prior to starting the therapy (antiviral therapy has to be stopped at least 7 days prior to initiation of the trial product).

4. General good health at the discretion of the investigator.
5. Willing to not use any topical genital therapy aside from the study device for the duration of the trial.
6. Willing to not use any systemic anti HSV therapy during the entire study starting 7 days prior to baseline.
7. Willing to obtain 2 swabs from external-genital areas once daily for the duration of the trial.
8. Willing to keep a daily trial diary during the treatment period.
9. Negative pregnancy test for women at screening.
10. Willing to use contraceptives for the duration of the study.
11. Subject must be willing and able (in the opinion of the investigator) to understand the patient information and informed consent form and to comply with the clinical trial protocol and procedures.
12. Subject must be willing to give written informed consent.

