5.2.2. Participant Screening - Visit 0-1

The screening of potential participants will be conducted by one or more study team members. The site research team will be responsible for ensuring and reporting screening of men and women for study eligibility. Cumulative screening and enrollment logs will be maintained by research sites. Reasons for screen failures will be documented in study logs.

All anti-viral therapies shall be stopped minimally 7 days prior to Visit 1.

Women that are more than 1 year post-menopausal will be considered as having no child bearing potential, and the pregnancy test and use of contraceptives is not applicable for them.

Table 2 lists the schedule of events for participants from the initial screening and baseline measures through their bi-weekly follow-up visits. These measures are more fully described in the subsequent sections.

Table 2. Schedule of Events

Activity	Treatment Period				
	Screening	Visit 1	FUP call	Visit 2	Visit 3
Informed Consent	X				
Review Inclusion/Exclusion Criteria	X				
Medical History (including HSV history)	X				
Interim History (including HSV history)		X		X	X
Targeted Physical Exam (including external genital exam)	X	X*		X*	X*
HSV serology	X				
Urine pregnancy test	X				
Provide Study Device and/or training		X	X	X	
Review device use adherence				X	X
AE assessment				→	
User Questionnaire					X
Daily Swab Collection & Diary				→	

* for women possibly including internal genital exam if symptomatic

The following screening data will be collected for all study subjects prior to enrollment to assess possible eligibility:

- Medical history, standard of care physical examination, including external genital exam

A subject will be considered as "enrolled", once (s)he has signed the Informed Consent. Study

specific data will not be collected for subjects who fail any of the eligibility criteria and do not apply the study product; these subjects will be recorded on a Screening Log where the reason for screening failure will be documented.

5.2.3. Treatment start - Visit 1

Once participant's eligibility is confirmed, i.e. HSV-2 serology is positive, select assessments and laboratory tests will be done prior to document baseline status. These include:

- Physical examination, including a genital examination that for women may include an internal genital examination if symptomatic;
- (Interim) medical history;
- Urine pregnancy test;
- Adverse Events assessment

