5.2.6. Genital herpes recurrence – Unscheduled visits

If a lesion develops that is consistent with genital herpes, swabs should be obtained from the lesion. Participants who have such a recurrence (i.e., papules, vesicles or pustules, ulcers, or crusts) during the treatment period are requested to contact and return to the clinic for an examination as soon as possible. That examination includes a genital examination, and for women may include an internal genital examination.

In case of a recurrence, participants will be instructed to apply their usual treatment or refer to their treating physician whichever is applicable, in order to receive treatment per standard practice. If the subject is successfully treated within 21 days, and meets the inclusion criteria and none of the exclusion criteria, subject may re-enter the study. The concerning follow-up period is prolonged with the number of days the treatment required. These visits shall be recorded as an unscheduled visit.

In case of a second recurrence, the subject shall exit the study.

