5.3. Follow-Up Visits

Visit	Exams	Visit window
0	Screening	Subject information and consent
1	Day 1	<21 days after ICF sign off
N/A	Day 3	2-5 days following visit 1

2	Day 14	12-16 days following Visit 1
3	Day 28	26-31 days following Visit 1

Upon Visit 1 and at each follow-up assessment, study staff will confirm the participant's availability for future follow-up and an appointment for the follow-up call will be made.

Planned absences from the area should be recorded to facilitate continued ability to contact a study participant. If a participant cannot be reached for a follow-up visit, the investigator will document on the follow-up data form, the efforts undertaken to contact the participant, referring physicians, family members, or other alternate contacts noted in the study participant's records. These efforts should include 3 attempts of telephone contacts at separate dates and times, and a registered letter.

If the participant cannot be reached in any way for their follow-up visits and misses the scheduled visit, new efforts will be undertaken to locate them at subsequent follow-up visits for safety purposes.

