8.1.3. Risks associated with study procedures

Study procedures may impose additional risks to study participants. In case of the SAFE Trial this theoretically could concern an increased risk for HSV infection of

- housemates, or
- other places than the extra-genital region

due to the frequent sampling and/ or touching of the extra-genital area.

HSV is transmitted via direct contact with infected secretions, such as during sexual intercourse. Casual contact, sharing of bathroom, toilet seats, etc. have not been implicated in HSV transmission. Furthermore, sampling and cream application is only done when participants are asymptomatic, which in principle is not different from normal hygienic or sexual behavior. Therefore, swabbing of the genital area by a study participant does not pose a risk to housemates.

The likelihood of spreading the virus to another part of the body is nil, since autoinoculation does not occur in persons who are infected outside of the primary episode as then immunity has been established. Of note, in that respect is that the University of Washington HSV research group has been using self-collected swabs for study of HSV for >25 years, and neither autoinoculation, nor exposure of housemates has ever been suspected as a result of these procedures.

In summary, the likelihood for imposing additional risks to study participants and their housemates due study procedures is considered negligible.

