Appendix 1: English master Informed Consent

Appendix 2: Daily Home PCR Instructions for Women

Thank you for volunteering for this study. Please read this sheet over carefully to understand how the study is being done.

Study Supplies

You will receive the following supplies:

- Dacron-tipped swabs (similar to Q-Tips®)
- Small plastic vials (with green, yellow, and red labels)
- Color coded labels
- A storage box
- VIBLOK cream
- Mirror
- A bag for transport
- A swab collection log
- A study diary

Sample Labels

The labels are preprinted with your study, clinic, and participant number. For each sample you collect, please fill in the date and time you collected the sample.

Study Diary

It is important that you bring your study diary to **each** clinic visit. Fill out the diary immediately before you obtain your swab samples. Please record this information as accurately as possible.

Storage of Samples

Vials with and without swabs can be stored at room temperature. When you return to the clinic for your next appointment, please bring the storage box with all the swab samples and your diary.

Communicating with the Clinic

If you develop symptoms of a recurrence or have any questions, please contact the **<specify the department>**. If you have ANY unusual urinary, genital, or rectal symptoms, such as a urinary tract infection, rash, or bleeding, call the clinic as soon as possible for an appointment. Every effort will be made to accommodate your schedule for clinic visits. Please call in at the earliest sign of symptoms so that a visit can be scheduled as soon as possible.

Weekdays: <specify contact information>

After Hours: <specify contact information>

Collecting Daily Swab Samples

Please read the following instructions carefully, it is very important that you collect samples in the same order as given in the instructions.

Please collect two extra-genital swabs per day: one **before** and one 5-60 minutes **after** VIBLOK application.

Please also collect a swab from a herpes **lesion** during an outbreak: do not apply VIBLOK when you develop a lesion and contact the clinic when you first notice symptoms.

Collect samples **once a day** before bathing or showering, or at least one hour after bathing or showering. Thoroughly wash and dry your hands before beginning.

[figure not shown]

Figure 2.1. Female genitals with VIBLOK application and swabbing area.

1/ To collect the **EXTRA GENITAL swab in the **green-labeled vial** **before** VIBLOK:**

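### SAP 5.1 reports the cream-free gap after a recurrence as VIBLOK exposure, and Protocol 5.2.6 credits only part of that gap to follow-up

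*Protocol*

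**What the plan says.** **Recurrence and re-entry.** Protocol 5.2.6 has a recurrence treated in the usual way and then allows one return: "If the subject is successfully treated within 21 days, and meets the inclusion criteria and none of the exclusion criteria, subject may re-enter the study". On follow-up it adds: "The concerning follow-up period is prolonged with the number of days the treatment required". A second recurrence ends participation.

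**No cream during a lesion.** Protocol 8.1.3 states that "sampling and cream application is only done when participants are asymptomatic". Appendix 2 tells women "do not apply VIBLOK when you develop a lesion and contact the clinic when you first notice symptoms", and Appendix 3 tells men the same.

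**Antiviral-free interval.** Inclusion criterion 3 (Protocol 4.1) says "antiviral therapy has to be stopped at least 7 days prior to initiation of the trial product". Protocol 5.2.2 says: "All anti-viral therapies shall be stopped minimally 7 days prior to Visit 1". Both rules refer to the start of the study; 5.2.6 does not mention the interval.

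**Length of use.** Protocol 5.3 places Visit 3 at "26-31 days following Visit 1". SAP 2.1 gives Day 26 to 31, with Visit 1 as Day 1, and has no entry for a prolonged follow-up. The Per Protocol set (Protocol 9.3, SAP 2.5.3) requires 26 or more days of application and does not say how days are counted. The synopsis speaks of "using VIBLOK for minimally 26 days in a row".

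**Exposure.** SAP 5.1 takes the days from Visit 1 to the last diary date on which a skin or a VIBLOK swab time was entered. It makes no deduction for interruptions.

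**The concern.** The plan requires a re-entrant to be off the cream for a time, yet the exposure rule counts that time as exposure. The primary endpoint is a safety endpoint and the data are meant to support CE marking, so the exposure summary is the context in which any count of device effects will be read. It should not include days when the protocol forbade use.

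The follow-up rule has a related gap. It returns treatment days but no other cream-free days. Lesion days before treatment are not returned, and neither is an antiviral-free interval if a site applies one. A participant who followed every instruction could then finish with fewer than 26 days of use and leave the Per Protocol set.

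The two rules also interact. SAP 2.5.3 does not define a day of application. If the SAP 5.1 span were used to decide membership, a person with 21 cream days could show 33 and be included; if cream days were used, the same person would be left out.

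**Working it through.** **Notation.** V is the day of Visit 3 before prolongation. T is treatment days (at most 21, Protocol 5.2.6). L is lesion days before treatment. G is cream-free days from an antiviral-free interval: 0 if none is applied, 7 if cream restarts on the eighth day after the last dose, 6 if on the seventh. I assume that the prolongation moves Visit 3 and its window by T, and that cream and swabs continue to the day of Visit 3.

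**1. The plan's own figure.** Without a recurrence, SAP numbering gives 26 cream days at Day 26, 28 at Day 28 and 31 at Day 31. The 26-day minimum is met across the window, and the SAP 5.1 span, counted inclusively, equals the days of use.

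**2. Re-entrant.**
- Reported exposure = V + T
- Cream-free days = T + L + G
- Cream days = (V + T) − (T + L + G) = V − L − G
- Excess = reported − cream = T + L + G

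**3. Exposure at nominal Visit 3 (V = 28, L = 0).** T = 5 and T = 10 are illustrations; 21 is the limit.

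| T | Reported | Cream days, G = 0 | Cream days, G = 6 or 7 | Excess, G = 0 | Excess, G = 6 or 7 |
|---|---|---|---|---|---|
| 5 | 33 | 28 | 22 or 21 | 5 | 11 or 12 |
| 10 | 38 | 28 | 22 or 21 | 10 | 16 or 17 |
| 21 | 49 | 28 | 22 or 21 | 21 | 27 or 28 |

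Each untreated lesion day adds one to the excess. If the span is taken as a plain difference of dates, reported exposure and excess are each one lower. The G = 0 columns need no assumption about the interval.

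**4. Cream days against the 26-day minimum.** T cancels, so the result is V − L − G.

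With G = 0: 26 − L at the earliest Visit 3, 28 − L at nominal, 31 − L at the latest.

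If the interval is re-applied, with L = 0:

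| Day count | G | Earliest | Nominal | Latest |
|---|---|---|---|---|
| SAP 2.1 (26, 28, 31) | 7 | 19 | 21 | 24 |
| SAP 2.1 (26, 28, 31) | 6 | 20 | 22 | 25 |
| Protocol 5.3, days following Visit 1 (27, 29, 32) | 7 | 20 | 22 | 25 |
| Protocol 5.3, days following Visit 1 (27, 29, 32) | 6 | 21 | 23 | 26 |

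Only the last cell reaches 26, and one untreated lesion day takes it to 25. All entries are one lower if no cream is applied on the day of Visit 3.

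**5. How late Visit 3 would have to be.** In the least favourable row (SAP count, G = 7, L = 0), 26 cream days need V = 26 + 7 = 33. That is Day 33 + T, two days past the prolonged window.

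**6. Primary analysis.** The As Treated set requires one application, so its membership does not change. The plan's 36 is confirmed: with no events the exact upper limit is 1 − 0.025^(1/36) = 9.74%, below 10%; with 35 it is 10.003%. Nothing above alters this.

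**The case against.** **The interval at re-entry is not in the plan.** Both 7-day rules are tied to study start. Criterion 6 asks for no systemic anti-HSV therapy throughout the study, so literal re-application of the inclusion criteria would bar anyone treated with an antiviral; the re-entry condition cannot be meant mechanically. The phrase about days required for treatment could also be read to cover the whole interruption. This stands. Without the interval only untreated lesion days go uncredited, so the 21-23 figure is conditional.

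**Scheduling can close the shortfall.** Three days lie between nominal Visit 3 and the end of the window, and SAP 2.2.1 allows that a visit a few days out of window need not cost any data. With no untreated lesion days, even the worst case is met at two days past the window. This stands too, but it relies on a site choosing a late visit that nothing in 5.2.6 or SAP 2.1 tells it to choose.

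**Exposure is only a label.** SAP 5.1 defines a first-to-last span, no test uses it, and interruptions appear elsewhere: days on anti-HSV medication and unscheduled visits (SAP 3.6), days with lesions (SAP 4.3.2). SAP 2.9 sends incomplete-diary handling to a separate plan that is not available here. All true, but none of those tables gives days of cream use, and nothing shows that the separate plan overrides an explicit definition.

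**Stronger readings.** A reader might infer that every re-entrant misses 26 days, or that the Per Protocol repeat of the primary analysis would fail. The documents support neither. They give no re-entry rate, no share treated with antivirals and no forecast of the Per Protocol set, so a fall below 36 is not shown. The three recurrences in criterion 3 are a minimum for past history and bound nothing here. The synopsis wording on consecutive days would exclude any re-entrant if applied strictly, but the Per Protocol definition does not repeat it.

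**Conclusion.** The exposure point holds as written in the plan. For each re-entrant, SAP 5.1 overstates VIBLOK use by about the number of treatment days, up to 21, plus any untreated lesion days and any antiviral-free days before restart. It depends only on treatment days being cream-free, which follows from the no-cream instructions and from the word re-enter in 5.2.6.

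The follow-up point is secondary and partly conditional. Untreated lesion days are uncredited on a literal reading. A further 6-7 days are uncredited only if sites re-apply the antiviral-free interval. In that case a re-entrant has about 21-23 cream days at nominal Visit 3 and 24-26 at the end of the window, and may miss the Per Protocol minimum unless Visit 3 is late.

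The As Treated success rule is untouched. The effect is confined to the exposure summary and Per Protocol membership, for a number of people that the documents do not allow one to estimate. It is worth correcting because the correction is cheap.

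**What to change.** **SAP 5.1 and 2.5.3.** Define days of VIBLOK use as the span less the documented interruption, from lesion onset to restart of the cream, and use the same count for the 26-day minimum. Diary times for the post-cream swab and returned packages should support the count but not serve as sole proof of application: the diary has no separate row for application, and a missed swab is not a missed application. This treats the 26 days as a total; if consecutive use is intended, 2.5.3 should say so.

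**Protocol 5.2.6 and SAP 2.1.** Prolong follow-up and move the Visit 3 window by all cream-free days from lesion onset to restart. State whether the 7-day antiviral-free interval applies at re-entry. With the whole gap credited, cream days at nominal Visit 3 return to 28 on SAP numbering (29 on the protocol count), whatever T, L and G are.

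**Cost.** One paragraph in 5.2.6 and short SAP edits, using data already collected. Reported exposure will be lower, and some re-entrants will stay up to about a week longer.

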5.3. Follow-Up Visits

Visit	Exams	Visit window
0	Screening	Subject information and consent
1	Day 1	<21 days after ICF sign off
N/A	Day 3	2-5 days following visit 1

2	Day 14	12-16 days following Visit 1
3	Day 28	26-31 days following Visit 1

Upon Visit 1 and at each follow-up assessment, study staff will confirm the participant's availability for future follow-up and an appointment for the follow-up call will be made.

Planned absences from the area should be recorded to facilitate continued ability to contact a study participant. If a participant cannot be reached for a follow-up visit, the investigator will document on the follow-up data form, the efforts undertaken to contact the participant, referring physicians, family members, or other alternate contacts noted in the study participant's records. These efforts should include 3 attempts of telephone contacts at separate dates and times, and a registered letter.

If the participant cannot be reached in any way for their follow-up visits and misses the scheduled visit, new efforts will be undertaken to locate them at subsequent follow-up visits for safety purposes.

5.3.1. Missed Visits

Participants who miss a follow-up visit will not be considered to be withdrawn from the trial and contact with the participant should continue to be established for the follow-up examinations if applicable. Every participant that started applying VIBLOK, should be encouraged to remain in the study until they have completed the protocol-required follow-up period. If the participant discontinues prematurely from the study, the reason for discontinuation must be documented on the appropriate case report form (CRF). Possible reasons for premature discontinuation may include, but are not limited to the following:

- Withdrawal of consent: Participant decides to withdraw from the study. If a participant withdraws from the clinical investigation, the reason(s) should be recorded. If such withdrawal is due to problems related to the investigational device safety, the investigator shall ask for the participant's permission to follow his/her status/condition outside the investigation.
- Lost to follow-up – All participants should be encouraged to return to the clinic for evaluation during follow-up. If a participant is unable to return to the clinic, 3 separate telephone calls (or emails) should be made to attempt to bring the participant back into the clinic or obtain safety information. All attempts should be documented in the source documents. If the participant does not respond to the 3 telephone calls then the Investigator should send a certified letter to the participant. If applicable, a new round of attempts to contact the participant for return to the clinic for evaluation should be made when the subsequent visit is due.

Patients who discontinue prematurely will be included in the analysis of results, and will not be replaced.

